9.1 Patient identification

Patients that will be approached for this study will have already been recruited for one of the two studies detailed below. They will have had a cognitive screen using the OCS-Bridge screening battery as part of either:

- 1. The Cognition Evaluation for patients with Neurological Tumours (the CogENT study) - REC reference: 18/LO/0491.
- 2. Assessing impact of surgically-induced deficits on patient functioning and quality of life (SIND study) - REC reference: 19/WM/0152.

Patients will be identified pre and post operatively from our Multi-Disciplinary Team (MDT) process.

It is important to identify patients with pre-existing defects of emotional recognition preoperatively as a further 20% of patients acquire temporary deficits post-operatively. Whereas our data from the CogENT study suggests patients with deficits pre-operatively do not improve at delayed assessment. This method of identifying potential patients will therefore help exclude patients that may get better without any rehabilitation. Patients scoring 11 or less on the emotional recognition test that are part of the OCS-Bridge battery are considered to have a deficit.

Patients will be approached either in a clinic or remotely by telephone (in accordance with Trust guidance concerning COVID-19). The study will be introduced to the patient and they will be provided with the patient information sheet. Patients will be given time to think about participating and will be followed up by phone call/further phone call. Patients who wish to take part will then be invited to give written consent at their next clinic visit. The patient's carers will also be approached about completing their own assessments. Carers who wish to take part will give written informed consent.

SCARF-BT Protocol IRAS: 270758 Version Number: 1.1

9.2 Study Screening

Only after the patient has consented to participate can the study specific assessments be performed.

The following assessments are required at screening:

- Informed consent
- Post-operative OCS-Bridge screening
- Personal details (Age at registration, Gender assigned at birth)
- Handedness
- Years in Education
- Age at leaving full time Education
- Clinical data:
 - WHO performance status (Refer to Appendix 2)
 - Histology of tumour and site of tumour
- Medical History (Disease Presentation, use of steroid and anti-epileptics to control symptoms)

9.3 Patient Registration

Registration of eligible patients will be performed prior to any baseline research assessments taking place. To register patients the delegated study team member will be required to, at a minimum, provide the following information:

- Age at registration
- Gender assigned at birth
- Date of informed consent
- Confirmation that eligibility criteria have been met

A unique patient identifier will be allocated for each individual patient.

9.4 Study assessments - Baseline

Post-operative assessments should be carried out within two weeks of surgery, and only after the patient has been registered these include:

- 1. Diagnostic Assessment of Non-verbal Accuracy-2, Adult Faces (DANVA2-AF)²⁰ a computerised test showing 24 photographs of 4 different facial expressions for 2.5 seconds each. Normative scores are available by age for this measure and an abnormal score is defined as ≥ 1 Standard deviation from the norm).
- 2. Part 1 of Emotion Recognition and Social Inference: The Awareness of Social Inference Test (TASIT) uses short one-minute video vignettes to assess emotion and social inferences. There are three subtests that comprise the TASIT: Emotional Evaluation Test (EET); the Social Inference-Minimal (SI-M); and Social Inference-Enriched (SI-E), but only the EET subtest will be used in this study. In the EET subtest, actors portray seven different emotions with dynamic facial movements, tone of voice, postures and gestures through short vignettes. These emotions include happy, sad, angry, disgust, fearful, surprised and neutral. We will use data from the EET subtest for our analyses As A and B tests exist, we will use both tests to avoid learning effect.
- 3. The Toronto Alexithymia Scale-20 (TAS-20) this is the most widely used selfreported questionnaire to measure alexithymia and is comprised of 3 factors: 1)

ability to identify emotions (e.g., I am often confused about what emotion I am feeling); 2) ability to describe emotions (e.g., It is difficult for me to find the right words for my feelings); and 3) externally-oriented thinking (e.g., I prefer to just let things happen rather than understand why they turned out that way).

- 4. Patient reported quality of life. (EORTC QCQ30 with the BN20)
- 5. Patient's families quality of life (Caregiver Quality of Life Index-Cancer (CQOLC)http://www.midss.org/content/caregiver-quality-life-index-cancer-cgolc-

Quality of life questionnaires will be completed before the clinic visit. If patients or their carers become distressed by the topics raised in the quality of life questionnaires, they will be supported by members of the clinical research team during their clinic visit.

Stage 1 will be used to define which of the assessments patients are able to complete. These assessments will be used for stage 2.

9.5 Randomisation

STAGE 1: This is a non-randomised study. All patients will undergo the FACES Intervention

STAGE 2: Patients will be randomised 1:1; half receiving the FACES intervention (active intervention) and the other half receiving the General Cognition Intervention (control intervention)

'A web-based central randomisation system supplied by Sealed Envelope will allocate the intervention.

9.6 Study Interventions

For both patient cohorts training on the use of the interventions will be provided. In Stage 1 all patients will receive the FACES intervention. In Stage 2 patients will be randomised to either FACES intervention or General Cognition Control Intervention.

Where necessary a computer will be provided to patients for the duration of the study to allow them to do the interventions.

9.6.1 FACES Intervention (active intervention)

This intervention has been previously described and validated in patients with traumatic brain injury¹⁷. In essence, the intervention will be a one-to-one computer-assisted treatment facilitated by an assistant psychologist who will have received training in administering the test. It will consist of 3 x 1-hour interventions each week for 3 weeks. This will be started post-operatively and continued until they start other treatments such as radiotherapy.

The program is designed so that difficulty is gradually increased throughout the intervention by using facial expressions ranging from obvious to subtle and through the use of vanishing cues (i.e., cues to guide participants' attention).

9.6.2 General Cognition Control Intervention (control intervention)

The purpose of the cognitive training intervention was to control for the one-on-one attention and personal interaction that participants in the treatment groups were

SCARF-BT Protocol IRAS: 270758 Version Number: 1.1

receiving, without providing any type of emotion-related training. Previous studies have confirmed a 'placebo effect' and the necessity of a control intervention¹⁷. Participants in Cognitive Training played a variety of online, publicly available computer games that targeted speed of processing, visual scanning, attention, memory, reasoning, and problem-solving skills.

9.7 Study Assessments - Post-Intervention

These assessments will be performed before the start of radiotherapy and after completing the three weeks of the intervention. Time points later than this will be confounded by effects of radiotherapy. These assessments will include:

- Diagnostic Assessment of Non-verbal Accuracy-2, Adult Faces (DANVA2-AF);
- 2. Part 1 (EET subtest) of Emotion Recognition and Social Inference (TASIT);
- 3. The Toronto Alexithymia Scale-20 (TAS-20).
- 4. Patient reported quality of life. (EORTC QCQ30 with the BN20)
- 5. Patient's families quality of life.(Caregiver Quality of Life Index-Cancer (CQOLC). http://www.midss.org/content/caregiver-quality-life-index-cancer-cgolc-scale

Quality of life questionnaires will be completed before the clinic visit. If patients or their carers become distressed by the topics raised in the quality of life questionnaires, they will be supported by members of the clinical research team during their clinic visit.

Stage 1 will be used to define which of the assessments that patients are able to complete. These assessments will be used for stage 2.

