7.4 Participants Study duration

Patients will participate in the study until the post intervention study assessments which will be performed prior to commencing radiotherapy (approximately six weeks following surgery).

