8.4 Subject withdrawal criteria

Patients may withdraw from the trial assessments or from the trial completely, at any time at their own request, or they may be withdrawn at any time at the discretion of the Investigator or Sponsor for safety, behavioural, or administrative reasons.

If the patient withdraws consent for disclosure of future information, no further evaluations should be performed and no additional data should be collected. The Study Management Group (SMG) may retain and continue to use any data collected before such withdrawal of consent.

Patients should be withdrawn from the study and replaced only if the patient requests to be withdrawn.

Procedures and assessments

Summary of the timings and assessments is listed below in the table - Section 9.9.

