9.10 Schedule of Assessments

Time Point	Study Screening		Baseline		INT-1	INT-2	INT-3	INT-4	INT-5	INT-6	INT-	INT-8	INT-9	Post -INT
Time Frame	<2 weeks post-op		<2 weeks post-op		Week 1	Week 1	Week 1	Week 2	Week 2	Week 2	Week 3	Week 3	Week 3	< 2 weeks before radiotherapy
Consent	Χ													
OCS-Bridge screening ¹	Х			Ra										
Medical History ²	Х	Re		and										
Clinical data ³	Х	Regist		lom										
DANVA2-AF ⁵			X	nisati										X
TASIT ⁶		ration	X	1 ti										X
TAS-20 ⁷		1 -	X	on ⁴										X
QoL questionnaire ⁸			Х											Х
Instruct patient9			X											X
INTERVENTION ¹⁰				1	Х	Х	Х	Х	Х	Х	Х	Х	Х	
Patient feedback ¹¹														X

- 1. Potential patients will be identified pre-operatively (as part of CogENT and SIND studies) for deficits using the OCS-Bridge screening tool., After consent, the OCS-Bridge screening tool will be used post-operatively during screening to ensure deficits remain
- 2. Medical history will include disease presentation, pre-existing neurological, psychiatric or hearing or visual problems that will prevent testing.
- 3. Clinical data will include performance status, histology of tumour, site of tumour.
- 4. Randomisation Stage 2 only
- 5. DANVA2-AF = Diagnostic Assessment of Non-verbal Accuracy-2, Adult Faces.
- 6. TASIT = The Assessment of Social Interference Test (Part 1)
- 7. TAS-20 = Toronto alexithymia scale.
- 8. Quality of life will be assessed using the EORTCQLQ-30 scale with the BN20 brain tumour module
- 9. Patients will be instructed to use the intervention a patient manual is available.
- 10. Intervention is either the Emotional Recognition Rehabilitation Intervention the Faces Intervention or General Cognition Control Intervention
- 11. A final patient feedback session will be offered to explain the patient's problems and strategies for dealing with this

10 Assessment of Safety

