11.2 Statistical methods

11.2.1 Stage 1- Criteria for Stop/Go decision prior to Stage 2

At the end of Stage 1 there will be an assessment made by the SMG as to whether the Stage 2 study should go ahead. This decision will be made on the following criteria:

- 1. Percentage of patients attending the Surgical Neuro-oncology Clinic that are screened for emotional recognition deficits pre-operatively?
- 2. Percentage of patients with a deficit that are approached for the study?
- 3. Percentage of patients recruited that can complete all the assessments?
- 4. Percentage patients recruited that are able to complete the FACES intervention adapted for remote delivery with the assistance of a psychologist.

As per the sample size calculations described above, less than 50% would be deemed unacceptable (see Sample Size calculation above).

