11.2.2 Stage 2 -Feasibility Assessments

- 1. To explore if we are able to screen patients with suspected high grade glioma attending clinic for deficits in emotional recognition. A deficit in emotional recognition is defined as scoring 11 or less on the emotional recognition test from the OCS-Bridge battery. To proceed with a larger, efficacy study we would need to be able to screen a minimum of 75% of new patients.
- 2. Acceptability will be assessed by calculating the percentage of screened patients that provided informed consent. The intervention will be considered feasible if at least 50% of patients meeting the eligibility criteria provided informed consent. This will be explored in more detail with the parallel qualitative study.
- 3. To Assess the compliance of the intervention and control arms, the percentage of patients who have completed all sessions will be calculated. Compliance will be concluded if at least 80% of patients complete all sessions.
- 4. Assess the acceptibility of the following established, validated outcome measures:
 - a. Diagnostic Assessment of Non-verbal Accuracy-2, Adult Faces (DANVA2-AF);
 - b. Part 1, which includes emotion recognition, of Emotion Recognition and Social Inference: The Awareness of Social Inference Test (TASIT);

IRAS: 270758 SCARF-BT Protocol Version Number: 1.1 c. The Toronto Alexithymia Scale-20 (TAS-20).

For each of these measures we will measure completion rates pre- and post-intervention. Acceptability will be explored further with our parrallel qualitative study.

- 5. To Assess the effect size of the intervention we will be assess changes in assessment measures (below) between the active (FACES) intervention group and the control group. Differences in scores will be assessed for:
 - a. DANVA 2-AF
 - b. TASIT using the TASIT version B at retest.
 - c. TAS-20 alexithymia.
 - d. QLQ30 and BN20 quality of life measures will be assessed using published minimal clinically important differences²⁵.
- 6. The difference between the Intervention group and the control group in Outcome Measures will be calculated together with 95% confidence interval. This will provide an early indicator that the intervention may make some difference and would be worth exploring in a larger, multicentre study as well as determining future sample sizes.

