11.3 Procedure to account for missing or spurious data

Missing data will be reported and the impact of missing data will be discussed and sensitivity analyses reported according to published standards²⁶. The missing data mechanism will be explored and multiple imputation may be applied as a sensitivity analysis compared to a complete case analysis as appropriate. Other sensitivity analyses will be performed in order to evaluate the robustness of the primary analyses.

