11.4 Definition of the end of the study

STAGE 1 will end either; when we understand the intervention and assessments are acceptable to patients and the technique is no longer evolving or; 10 patients have been recruited and undergone their final assessment – whichever is soonest.

Although we expect to screen more patients (up to a maximum of 20), we expect to recruit up to 10 patients to go forwards to the intervention at this stage.

The Study Management Group will look at the data from the patients completing stage 1 to make a decision whether to stop after stage 1 or to continue to stage 2 (See section 11.2.1)

STAGE 2 will end when 19 evaluable patients per arm (intervention and control arms) have undergone their final assessment.

12 Data handling and record keeping

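### Section 9.7, read literally, ties the post-intervention assessment to completing the intervention; other sections do not, and none says whether patients who stop training are assessed

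*Protocol*

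**What the plan says.** Protocol section 9.7 is the procedural text for the outcome visit (DANVA2-AF, TASIT EET, TAS-20, EORTC questionnaires, CQOLC). It sets two conditions together: "These assessments will be performed before the start of radiotherapy and after completing the three weeks of the intervention".

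Other sections time the same visit without the second condition:
- The schedule in 9.10 gives its time frame as "< 2 weeks before radiotherapy", and the synopsis does likewise.
- Section 7.4: "Patients will participate in the study until the post intervention study assessments which will be performed prior to commencing radiotherapy".
- Section 8.4: "Patients should be withdrawn from the study and replaced only if the patient requests to be withdrawn". It treats withdrawal from trial assessments as something the patient may request. Stopping the sessions is not listed as a trigger.

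The results of the visit are used in four places:
- Section 11.2.2 items 5 and 6: the between-arm score differences with 95% confidence intervals, meant as an early indicator and for planning a later sample size.
- Section 11.2.2 item 4: "For each of these measures we will measure completion rates pre- and post-intervention".
- Section 11.2.1 criterion 3 (Stage 1 stop/go): "Percentage of patients recruited that can complete all the assessments". Criterion 4 is the percentage able to complete FACES. Below 50% is unacceptable.
- Section 11.4: "STAGE 2 will end when 19 evaluable patients per arm (intervention and control arms) have undergone their final assessment". Evaluable is not defined.

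On missing scores, section 11.3 says that "multiple imputation may be applied as a sensitivity analysis compared to a complete case analysis as appropriate".

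**The concern.** The protocol expects some patients to stop: section 11.2.2 accepts compliance at 80% completing all sessions, and section 11.1.2 concludes feasibility at 50%. It does not say whether those patients are retested, and the sentence that staff would follow suggests that they are not.

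Two results are exposed. The first is the score difference. If only finishers are scored, randomisation no longer protects the comparison. Stopping may go with deterioration and may differ between arms. This matters because the estimate is to inform whether a larger trial is worthwhile and how large it should be.

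The second is stop/go criterion 3. Its denominator is all recruited patients. If patients who stop the course are not tested, they fail criterion 3 for the same reason that they fail criterion 4. Sections 9.4 and 9.7 also use Stage 1 to choose the Stage 2 instruments, so a usable test could be dropped because of the course rather than the test.

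An analysis plan can choose the analysis population but cannot supply scores that were not collected. Section 9.7 itself says that later time points are confounded by radiotherapy.

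**Working it through.** **The passages together.** Take a patient who stops after, say, five sessions, does not ask to withdraw, and has not started radiotherapy. Under 7.4, 8.4 and 9.10 the patient is still in the study and the visit is due. Under 9.7 read literally, the second condition is not met. The sections give different answers, and none addresses the case directly.

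**Bias in the score difference if only finishers are scored.** The protocol gives no expected completion rate by arm, no correlation and no SD, so these inputs are assumptions. Let Z be a standard normal propensity to complete, with correlation r to the outcome, and let the top fraction p of each arm finish. Then E(Z | finish) = φ(z)/p, where z is the (1 − p) quantile, and with no true effect

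bias (FACES − control) = r × [E(Z | p_FACES) − E(Z | p_control)], in SD units.

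- p = 0.80: φ(−0.8416)/0.80 = 0.2800/0.80 = 0.350.
- p = 0.95: φ(−1.6449)/0.95 = 0.1031/0.95 = 0.109.
- 80% v 95%: difference 0.241; r = 0.3 gives 0.072 SD and r = 0.5 gives 0.121 SD.
- 65% v 90%: 0.570 − 0.195 = 0.375, giving 0.112 to 0.187 SD.
- Equal completion: 0.

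A different assumption agrees in order of size. If finishers change D SD more than stoppers, the bias is D × [(1 − p_FACES) − (1 − p_control)]. For 80% v 95% and D from 0.25 to 1.0, this is 0.15 × D = 0.04 to 0.15 SD.

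**Precision.** The half-width of the 95% interval is 1.96 × √(2/n) SD. With n = 19 per arm it is 0.64 SD. With 80% scored, n = 15.2 and it is 0.71 SD. Some precision is therefore lost even when the arms complete equally.

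**Numbers to randomise.** If evaluable means having a final assessment and only finishers have one, 19 per arm at 80% completion needs 19/0.80 = 23.75, so 24 randomised per arm. Section 7.3 plans 19.

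**Stop/go criterion 3 with 10 patients.** Assume that 60% finish the course and 80% of finishers can do all the tests. Failing means 4 or fewer of 10.

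| Stoppers | Rate per recruited patient | P(4 or fewer of 10) |
|---|---|---|
| Not tested | 0.6 × 0.8 = 0.48 | 0.427 |
| Tested, able at half the finishers' rate (40%) | 0.48 + 0.4 × 0.4 = 0.64 | 0.107 |
| Tested, as able as finishers (80%) | 0.48 + 0.4 × 0.8 = 0.80 | 0.006 |

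The last row is a best case. The gain from testing stoppers depends on how well they can do the tests. If 80% finish and stoppers are not tested, the rate is 0.8 × 0.8 = 0.64 and the chance of failing is again 0.107.

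**The case against.** The strongest reply is that 9.7 sets a time window and not a condition on the patient. Its next sentence explains the timing by radiotherapy. When the protocol means adherence it counts sessions, as in the Stage 1 definition of completing all nine, so three weeks can be read as calendar time. With 7.4, 8.4 and 9.10, a patient who stops training would then be due the visit. This stands. A reader might infer that the trial assesses only completers by design, but the documents do not support that: no section says that stoppers go untested or that the comparison is limited to completers. What remains is that 9.7 can reasonably be read the other way and that nothing settles it.

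Three further objections have force:
- The bias figures rest on inputs that are not in the protocol. The 65% v 90% case puts FACES below the 80% needed to proceed, so the trial would already have missed that criterion.
- A reader might take the contrast of 43% and 0.6% for criterion 3 as the effect of the wording. It assumes that stoppers test as well as finishers, which sits badly with the idea that stopping tracks deterioration.
- Section 11.3 already promises to report missing data and run sensitivity analyses. The analysis set and the Stage 2 completion denominators may properly be left to an analysis plan.

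None of these replaces a score that was not collected in the window.

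**Conclusion.** The point holds as an inconsistency about who is assessed. Section 9.7 read literally requires completion, 7.4, 8.4 and 9.10 do not, and patients who stop training are not provided for.

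The consequence follows only if sites apply 9.7 literally. Then the score difference moves towards a completer comparison, with an assumed bias of about 0.07 to 0.12 SD at 80% v 95% completion and correlation 0.3 to 0.5, and about zero with equal completion. This is small beside an interval half-width of about 0.64 SD in an exploratory comparison, but it would carry into the planning of a later trial. Criterion 3 would partly double-count criterion 4, by an amount that depends on how well stoppers can do the tests. The session-completion criterion is unaffected. The change is worth making because it is cheap and the loss cannot be repaired later.

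**What to change.** Reword section 9.7 along these lines: the post-intervention assessments are offered to every registered (Stage 1) or randomised (Stage 2) patient who has not withdrawn from assessments, at the end of the planned three weeks and before radiotherapy, whatever the number of sessions attended. Define evaluable in 11.4, and in the matching synopsis text, so that it does not depend on sessions attended.

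The cost is a wording amendment plus a visit already on the schedule for the patients who stop training. No new test or time point is needed. The small downside is that some of these patients will decline. Recording this separates a declined assessment from one that was never offered.
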